7 DOSING DELAYS/DOSE MODIFICATIONS

7.1 Recording Dose Delays and Omissions

All dosing delays and omissions will be recorded in the source documents and captured in the OnCore database.

7.2 Toxicity Grading

AEs will be characterized and graded according to NCI CTCAE v5.0.

7.3 Lenvatinib Treatment Modification

Dose modifications for lenvatinib are based on current prescribing information.

Recommendations for lenvatinib dose interruption, reduction and discontinuation for adverse reactions are listed in [Table 2](#). [Table 3](#) lists the recommended dosage reductions of lenvatinib for adverse reactions.

Table 2: Recommended Dosage Modifications for Lenvatinib

Adverse Reaction	Severity	Dosage Modifications for Lenvatinib
Hypertension	Grade 3	
 Withhold for grade 3 that persists despite optimal antihypertensive therapy. Resume at reduced dose when hypertension is controlled at less than or equal to grade 2.
	Grade 4	
 Permanently discontinue.
Cardiac Dysfunction	Grade 3	
 Withhold until improves to grade 0 to 1 or baseline. Resume at a reduced dose or discontinue depending on the severity and persistence of adverse reaction.
	Grade 4	
 Permanently discontinue.
Arterial Thromboembolic Event	Any Grade	
 Permanently discontinue.
Hepatotoxicity	Grade 3 or 4	
 Withhold until improves to grade 0 to 1 or baseline. Either resume at a reduced dose or discontinue depending on severity and persistence of hepatotoxicity. Permanently discontinue for hepatic failure.
Renal Failure or Impairment	Grade 3 or 4	
 Withhold until improves to grade 0 to 1 or baseline. Resume at a reduced dose or discontinue depending on severity and persistence of renal impairment.

Table 3: Recommended Dosage Reduction Steps for Lenvatinib

First Dosage Reduction	Second Dosage Reduction	Third Dosage Reduction
14 mg once daily	10 mg once daily	8 mg once daily

7.3.1 Dosage Modifications for Severe Renal Impairment

The recommended dosage of lenvatinib for patients with endometrial carcinoma and severe renal impairment (creatinine clearance less than 30 mL/min calculated by Cockcroft-Gault equation using actual body weight) is 10 mg orally once daily.

7.3.2 Dosage Modifications for Severe Hepatic Impairment

The recommended dosage of lenvatinib for patients with endometrial carcinoma and severe hepatic impairment (Child-Pugh C) is 10 mg taken orally once daily.

7.3.3 General Guidelines for Holding Periods of Lenvatinib due to Procedures

For minor procedures, lenvatinib should be stopped 2 days before the procedure and restarted 2 days after, once there is evidence of adequate healing and no risk of

bleeding. Needle biopsies (fine needle aspirations and core needle aspiration) are usually considered minor procedures.

For major procedures, lenvatinib should be stopped 1 week (5 half-lives) before the procedure and then restarted once there is clear wound healing and no risk of bleeding, but at least 1 week after the procedure. It is up to the investigator to determine if it is a major or minor procedure. Usually a major procedure implies general anesthesia.

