6.3 General Concomitant Medication and Supportive Care Guidelines

- Patients should receive appropriate supportive care measures as deemed necessary by the treating physician and according to the current prescribing information for each agent.
- Patients may be premedicated for nausea and vomiting. Choice of antiemetic is at the treating physician's discretion with the exception that steroids are NOT permitted.
- Refer to [Table 1](#) for management of infusion reactions.

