Hypocalcemia: Monitor blood calcium levels at least monthly and replace calcium as necessary. Withhold and resume at reduced dose upon recovery or permanently discontinue lenvatinib depending on severity.

Reversible Posterior Leukoencephalopathy Syndrome: Withhold and resume at a reduced dose upon recovery or permanently discontinue lenvatinib depending on severity and persistence of neurologic symptoms.

Hemorrhagic Events: Serious including fatal hemorrhagic events can occur with lenvatinib. Consider the risk of severe or fatal hemorrhage associated with tumor invasion or infiltration of major blood vessels (e.g., carotid artery). Withhold and resume at reduced dose upon recovery or permanently discontinue lenvatinib based on the severity.

Impairment of Thyroid Stimulating Hormone Suppression/Thyroid Dysfunction: Lenvatinib impairs exogenous thyroid suppression. Monitor thyroid function prior to initiating lenvatinib and at least monthly during treatment. Treat hypothyroidism according to standard medical practice.

Impaired Wound Healing: Impaired wound healing has been reported in patients who received lenvatinib. Withhold lenvatinib for at least 1 week prior to elective surgery. Do not administer for at least 2 weeks following major surgery and until adequate wound healing. The safety of resumption of lenvatinib after resolution of wound healing complications has not been established.

Osteonecrosis of the Jaw Osteonecrosis of the Jaw (ONJ): ONJ has been reported in patients receiving lenvatinib. Perform an oral examination prior to treatment with lenvatinib and periodically during lenvatinib treatment. Consider preventive dentistry prior to treatment with lenvatinib. Avoid invasive dental procedures, if possible, particularly in patients at higher risk. Withhold lenvatinib for at least 1 week prior to scheduled dental surgery or invasive dental procedures, if possible. Withhold lenvatinib if ONJ develops and restart based on clinical judgment of adequate resolution.

Embryofetal Toxicity: Lenvatinib can cause fetal harm. Advise of potential risk to a fetus and use of effective contraception during treatment and for at least 30 days after the last dose.

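### Section 7.3.3 permits a 2-day lenvatinib hold before elective surgery classed as minor; section 9.1.9 asks for at least 1 week, and nothing says which applies

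*Combined protocol and SAP*

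**What the plan says.** Section 7.3.3 is the protocol's guidance on interrupting lenvatinib for procedures, and it has two classes.

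- **Minor:** "For minor procedures, lenvatinib should be stopped 2 days before the procedure and restarted 2 days after, once there is evidence of adequate healing". Restart also requires that there be no bleeding risk. The only example given is needle biopsy.
- **Major:** "lenvatinib should be stopped 1 week (5 half-lives) before the procedure". Restart comes no sooner than 1 week afterwards, once the wound has clearly healed.

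On choosing between the classes it says "It is up to the investigator to determine if it is a major or minor procedure", with one cue: "Usually a major procedure implies general anesthesia".

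Section 9.1.9 covers the same ground in its paragraph on impaired wound healing: "Withhold lenvatinib for at least 1 week prior to elective surgery". That sentence mentions neither the size of the operation nor the anesthetic. The next sentence, on the period after surgery, is limited to major surgery.

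Footnote S of the study calendar (section 12) sends sites to sections 6.2, 7.3 and 9.1 for lenvatinib instructions. Section 7.3 says its dose modifications rest on current prescribing information, and section 9.1 says it is drawn from the July 2021 label. Section 6.3 asks for supportive care "according to the current prescribing information for each agent". None of these states an order of precedence between 7.3.3 and 9.1.9.

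**The concern.** The two sections sort operations differently. Section 9.1.9 asks whether the surgery is elective. Section 7.3.3 asks whether the procedure is major or minor, and offers anesthesia as the usual guide. An elective operation under local or regional anesthesia is elective for 9.1.9 and may be minor for 7.3.3. A site that classes it so and stops lenvatinib 2 days beforehand has followed 7.3.3 and fallen short of 9.1.9.

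What is at stake is patient safety and consistent practice across up to 10 sites. The 1-week hold in 9.1.9 is there because of impaired wound healing. The healing and bleeding conditions in 7.3.3 apply to restarting the drug, so they cannot lengthen a hold that ended when the operation took place. The objective response rate (ORR) analysis and the sample size are not touched.

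**Working it through.** This is mainly a comparison of texts. The arithmetic only sizes the gap.

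**Inputs.** Minor hold 2 days, major hold 1 week described as 5 half-lives (7.3.3). Hold before elective surgery at least 1 week (9.1.9). Terminal half-life about 28 hours (9.1.7). One lenvatinib dose a day in 21-day cycles (6.2). Adherence means at least 80% of planned doses in a cycle (6.7).

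**The plan's own figure.** 5 × 28 h = 140 h, and 140 / 24 = 5.8 days. Rounded up to 1 week, this agrees with 7.3.3.

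**What each section gives before surgery.**

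| Situation | 7.3.3 | 9.1.9 | Agree? |
|---|---|---|---|
| Elective surgery classed as major | 1 week | at least 1 week | Yes |
| Elective surgery classed as minor | 2 days | at least 1 week | No |
| Needle biopsy | 2 days | not named; need not count as elective surgery | No clear conflict |

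Only the second row is in conflict.

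**Size of the gap.**
- Days: 7 − 2 = 5.
- Half-lives: 48 / 28 = 1.7 against 168 / 28 = 6.0.

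**Doses missed.** Take the operation as day 0, with restart at the earliest on day +2 in both cases.
- 2-day hold: days −2 to +1, 4 doses missed; 17 / 21 = 81.0% taken.
- 1-week hold: days −7 to +1, 9 doses missed; 12 / 21 = 57.1% taken.
- Difference: 9 − 4 = 5 doses; 5 / 21 = 23.8% of a cycle.

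The percentages assume that the whole hold falls in one cycle and that held doses still count as planned. The documents do not say whether they do. On those assumptions, the longer hold takes a patient from just above the 80% line to below it. Section 6.7 exempts only doses omitted for adverse-event management.

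**The case against.** The best reply is that the sections can be read together. Section 7.3.3 nowhere sets 2 days for elective surgery. It is headed as general guidance, its only minor example is needle biopsy, and its anesthesia cue is hedged. Section 9.1.9 is specific and sets a minimum. A site that consults both, as footnote S directs, can hold 1 week for elective surgery and 2 days for a biopsy. An investigator may also class surgery under local anesthesia as major, which gives 1 week under either section. Much of this stands: the conflict is conditional, and a careful site avoids it. What remains is that a site can comply with 7.3.3 and still fall below 9.1.9, and no sentence tells it otherwise. A shared basis in the label is not a precedence rule.

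Two stronger readings are tempting.

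- A reader might infer that 7.3.3 prescribes the short hold for any operation without general anesthesia. It does not; it leaves the choice open.
- A reader might add dental work, because 9.1.9 also says "Withhold lenvatinib for at least 1 week prior to scheduled dental surgery or invasive dental procedures, if possible", after "Avoid invasive dental procedures, if possible, particularly in patients at higher risk". The hold there is asked for only where possible, so a shorter one does not breach the text. That is not a conflict.

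It is also fair to say that no harm has been quantified. The documents link no length of hold to a rate of wound complications, and the half-life figures describe only the hold.

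**Conclusion.** The inconsistency is real but narrow, and its severity is minor. Section 7.3.3 permits, without requiring, a hold 5 days shorter than the minimum in 9.1.9 when an elective operation is classed as minor. This rests on the wording alone: investigator discretion and a non-binding anesthesia cue in 7.3.3, an unqualified sentence in 9.1.9, and no ranking of the two.

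The documents do not say how many patients will have such an operation on treatment, so no frequency or excess risk is claimed. Needle biopsies, procedures classed as major and the ORR estimate are unaffected.

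The restart after major surgery also differs, at least 1 week in 7.3.3 against at least 2 weeks in 9.1.9. That is a separate matter, does not depend on the minor class, and carries no weight here.

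**What to change.** Amend 7.3.3 to state that:

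1. any elective surgery is preceded by a lenvatinib hold of at least 1 week, whatever the anesthesia and whichever class the investigator assigns;
2. the 2-day hold is for needle biopsies and similar non-surgical procedures;
3. where 7.3.3 and 9.1.9 give different holds before a procedure, the longer one applies.

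The third statement should be confined to the pre-procedure hold. Making 9.1.9 govern throughout would also change the restart after major surgery, which deserves its own decision, and would give a July 2021 summary priority over a section meant to follow the current label. Some judgement remains over what counts as similar and non-surgical; the longer-hold rule limits its effect.

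Add to 6.7 that doses held for a procedure do not count towards nonadherence. Without this, a correct 1-week hold could be recorded as nonadherence, although the only stated consequence is re-instruction.

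The cost is a few sentences in an amendment, a memo to sites, and about 5 more missed daily doses per affected operation.

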7.4 Pembrolizumab Treatment Modification

Dose modifications for pembrolizumab are based on current prescribing information.

No dose reduction for pembrolizumab is recommended. In general, withhold pembrolizumab for severe (grade 3) immune-mediated adverse reactions. Permanently discontinue pembrolizumab for life-threatening (grade 4) immune-mediated adverse reactions, recurrent severe (grade 3) immune-mediated reactions that require systemic immunosuppressive treatment, or an inability to reduce corticosteroid dose to 10 mg or less of prednisone or equivalent per day within 12 weeks of initiating steroids.

Dosage modifications for pembrolizumab for adverse reactions that require management different from these general guidelines are summarized in [Table 4](#).

Table 4: Recommended Dosage Modifications for Pembrolizumab

Adverse Reaction	Severity*	Dosage Modification
Immune-Mediated Adverse Reactions		
Pneumonitis	Grade 2	Withhold†
	Grade 3 or 4	Permanently discontinue
Colitis	Grade 2 or 3	Withhold†
	Grade 4	Permanently discontinue
Hepatitis with no tumor involvement of the liver	AST or ALT increases to more than 3 and up to 8 times ULN or Total bilirubin increases to more than 1.5 and up to 3 times ULN	Withhold†
	AST or ALT increases to more than 8 times ULN or Total bilirubin increases to more than 3 times ULN	Permanently discontinue
Hepatitis with tumor involvement of the liver‡	Baseline AST or ALT is more than 1 and up to 3 times ULN and increases to more than 5 and up to 10 times ULN or Baseline AST or ALT is more than 3 and up to 5 times ULN and increases to more than 8 and up to 10 times ULN	Withhold†
	ALT or AST increases to more than 10 times ULN or Total bilirubin increases to more than 3 times ULN	Permanently discontinue
Endocrinopathies	Grade 3 or 4	Withhold until clinically stable or permanently discontinue depending on severity
Nephritis with Renal Dysfunction	Grade 2 or 3 increased blood creatinine	Withhold†
	Grade 4 increased blood creatinine	Permanently discontinue
Exfoliative Dermatologic Conditions	Suspected SJS, TEN, or DRESS	Withhold†
	Confirmed SJS, TEN, or DRESS	Permanently discontinue
Myocarditis	Grade 2, 3, or 4	Permanently discontinue
Neurological Toxicities	Grade 2	Withhold†
	Grade 3 or 4	Permanently discontinue
Hematologic toxicity in patients with cHL or PMBCL	Grade 4	Withhold until resolution to Grades 0 or 1
Other Adverse Reactions		
Infusion-related reactions	Grade 1 or 2	Interrupt or slow the rate of infusion
	Grade 3 or 4	Permanently discontinue

† Resume in patients with complete or partial resolution (grades 0 to 1) after corticosteroid taper. Permanently discontinue if no complete or partial resolution within 12 weeks of initiating steroids or inability to reduce prednisone to 10 mg per day or less (or equivalent) within 12 weeks of initiating steroids.

‡ If AST and ALT are less than or equal to ULN at baseline, withhold or permanently discontinue pembrolizumab based on recommendations for hepatitis with no liver involvement.

ALT = alanine aminotransferase, AST = aspartate aminotransferase, DRESS = Drug Rash with Eosinophilia and Systemic Symptoms, SJS = Stevens-Johnson Syndrome, TEN = toxic epidermal necrolysis, ULN = upper limit normal

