APPENDIX 1. PERFORMANCE STATUS CRITERIA

ECOG Performance Status Scale		Karnofsky Performance Scale	
Grade	Description	Percent	Description
0	Normal activity. Fully active, able to carry on all pre-disease performance without restriction.	100	Normal, no complaints, no evidence of disease.
		90	Able to carry on normal activity; minor signs or symptoms of disease.
1	Symptoms, but ambulatory. Restricted in physically strenuous activity, but ambulatory and able to carry out work of a light or sedentary nature (eg, light housework, office work).	80	Normal activity with effort; some signs or symptoms of disease.
		70	Cares for self; unable to carry on normal activity or to do active work.
2	In bed < 50% of the time. Ambulatory and capable of all self-care, but unable to carry out any work activities. Up and about > 50% of waking hours.	60	Requires occasional assistance, but is able to care for most of his/her needs.
		50	Requires considerable assistance and frequent medical care.
3	In bed > 50% of the time. Capable of only limited self-care, confined to bed or chair > 50% of waking hours.	40	Disabled; requires special care and assistance.
		30	Severely disabled; hospitalization indicated. Death not imminent.
4	100% bedridden. Completely disabled. Cannot carry on any self-care. Totally confined to bed or chair.	20	Very sick, hospitalization indicated. Death not imminent.
		10	Moribund, fatal processes progressing rapidly.
5	Dead.	0	Dead.

APPENDIX 2. DOSE MODIFICATION AND TOXICITY MANAGEMENT FOR IMMUNE-RELATED ADVERSE EVENTS (irAEs) ASSOCIATED WITH PEMBROLIZUMAB

Immune-related Adverse Event	Toxicity Grade or Conditions (CTCAE v4.0)	Action Taken with Pembrolizumab	irAE Management with Corticosteroids and Other Therapies	Monitor and Follow-up
General instructions:				
Corticosteroid taper should be initiated upon AE improving to Grade 0 or 1 and continue to taper over at least 4 weeks. For situations where pembrolizumab has been withheld, pembrolizumab can be resumed after AE has improved to grade 0 or 1 and corticosteroid has been tapered. Pembrolizumab should be permanently discontinued if AE does not resolve within 12 weeks of last dose or corticosteroids cannot be reduced to ≤ 10 mg prednisone or equivalent per day within 12 weeks.				

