Hypothyroidism	Grade 2-4	Continue	Initiate thyroid replacement hormones (e.g., levothyroxine or liothyroinine) per standard of care	Monitor for signs and symptoms of thyroid disorders.
Nephritis and Renal dysfunction	Grade 2	Withhold	Administer corticosteroids (prednisone 1-2 mg/kg or equivalent) followed by taper	Monitor changes of renal function.
	Grade 3 or 4	Permanently discontinue		
Myocarditis	Grade 1 or 2	Withhold	Based on severity of AE administer corticosteroids	Ensure adequate evaluation to confirm etiology and/or exclude other causes.
	Grade 3 or 4	Permanently discontinue		
All other immune-related AEs	Intolerable/persistent grade 2	Withhold	Based on type and severity of AE administer corticosteroids	Ensure adequate evaluation to confirm etiology and/or exclude other causes.
	Grade 3	Withhold or discontinue based on the type of event. Events that require discontinuation include but are not limited to: Gullain-Barre Syndrome, encephalitis		

Immune-related Adverse Event	Toxicity Grade or Conditions (CTCAE v4.0)	Action Taken with Pembrolizumab	irAE Management with Corticosteroids and Other Therapies	Monitor and Follow-up
	Grade 4 or recurrent grade 3	Permanently discontinue		

Withholding or permanently discontinuing pembrolizumab is at the discretion of the investigator or treating physician.

For patients with grade 3 or 4 immune-related endocrinopathy where withholding of pembrolizumab is required, pembrolizumab may be resumed when the AE improves to grade ≤ 2 and is controlled with hormonal replacement therapy or metabolic control is achieved (in the case of T1DM).

AE = adverse event, CTCAE = Common Terminology Criteria for Adverse Events, ALT = alanine aminotransferase, AST = aspartate aminotransferase, GI = gastrointestinal, irAE = immune-related adverse event, IV = intravenous, T1DM = Type 1 diabetes mellitus.

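### Table 4 and Appendix 2 give incompatible pembrolizumab instructions for grade 2 myocarditis and grade 3 nephritis, and no text says which governs

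*Combined protocol and SAP*

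**What the plan says.** Section 7.4 opens by naming its source: "Dose modifications for pembrolizumab are based on current prescribing information". It then gives a general rule, which is to withhold for grade 3 immune-mediated reactions and stop for grade 4, and sends the reader to Table 4 for reactions managed differently.

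Table 4, nephritis: the withhold row reads "Grade 2 or 3 increased blood creatinine", and only grade 4 leads to permanent discontinuation. The footnote on that row says "Resume in patients with complete or partial resolution (grades 0 to 1) after corticosteroid taper".

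Table 4, myocarditis: "Myocarditis Grade 2, 3, or 4 Permanently discontinue".

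Appendix 2, nephritis: "Nephritis and Renal dysfunction Grade 2 Withhold". The next line of that row stops the drug permanently at grade 3 or 4.

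Appendix 2, myocarditis: "Myocarditis Grade 1 or 2 Withhold", with a permanent stop at grade 3 or 4. Its general instructions say of withheld drug that "pembrolizumab can be resumed after AE has improved to grade 0 or 1 and corticosteroid has been tapered".

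Section 6.3.1 cites Appendix 2 for supportive care of immune-related events. The title of Appendix 2, however, covers dose modification as well as toxicity management. The table has its own column for the action taken with pembrolizumab. A closing note leaves withholding or stopping to the discretion of the investigator or treating physician.

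**The concern.** In these two cells the instructions differ between a temporary hold with possible rechallenge and a permanent stop. Two physicians who each follow the protocol could treat the same patient differently.

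Myocarditis is the more serious case. Table 4 treats grade 2 as reason enough never to give the drug again, yet Appendix 2 leaves a restart open. In the nephritis cell, a patient who has recovered from grade 3 keeps or loses the drug according to which table the site opened.

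Up to 10 sites apply these rules. The decisions also feed secondary endpoint 3.3.3 (patients who discontinue because of treatment-related AEs) and the time-to-discontinuation analysis in Section 13.1.

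**Working it through.** The plan gives no figure to reproduce here, so the check is a row-by-row comparison followed by a search for a precedence rule.

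**1. The two tables side by side**

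| Event and grade | Table 4 | Appendix 2 | Result |
|---|---|---|---|
| Myocarditis, grade 2 | Permanent stop | Withhold, may resume | Conflict |
| Myocarditis, grade 3 or 4 | Permanent stop | Permanent stop | Agree |
| Nephritis, grade 2 | Withhold | Withhold | Agree |
| Nephritis, grade 3 | Withhold, resume on recovery | Permanent stop | Conflict |
| Nephritis, grade 4 | Permanent stop | Permanent stop | Agree |
| Colitis, grades 2 to 4 | Withhold at 2 or 3, stop at 4 | Same | Agree |
| Pneumonitis, first episode, grades 2 to 4 | Withhold at 2, stop at 3 or 4 | Same | Agree |
| Grade 1 myocarditis; recurrent grade 2 pneumonitis | Silent | Has a rule | Complementary |
| Hepatic | Multiples of ULN | Grades | Not comparable from the documents |

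There are two conflicts. Table 4 is the stricter for myocarditis and Appendix 2 is the stricter for nephritis, so neither table can serve throughout as the cautious one.

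**2. Precedence**

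- Section 7.4 points to prescribing information and Table 4, and does not mention Appendix 2.
- The general rule in 7.4 (withhold at grade 3) agrees with Table 4 on nephritis.
- Section 6.3.1 assigns Appendix 2 to supportive care.
- The Appendix 2 discretion note ranks neither table.

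The first three points favour Table 4 by inference. None states that it prevails.

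**3. A related difference: the 12-week limit on resolution of the event**

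The Table 4 footnote counts from the start of steroids, and Appendix 2 counts from the last dose. If last dose means the last pembrolizumab infusion, the Appendix 2 limit falls earlier by the number of days from that infusion to steroid start. On the nominal 21-day cycle with no dose held, that is 0 to 21 days. The ±3-day visit window can add 3 days (21 + 3 = 24) if it applies to the interval, or 6 days (21 + 3 + 3 = 27) if it applies to each scheduled Day 1.

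**4. Size for endpoint 3.3.3**

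One patient out of the planned maximum of 100 is 1/100 = 1 percentage point. Using Appendix 2 instead of Table 4 gives at most one fewer discontinuation per grade 2 myocarditis and at most one more per grade 3 nephritis, so the two cells push in opposite directions. The documents give no rate for either cell. Section 9.2.10 lists myocarditis under 1%, but for pembrolizumab or other antibodies of its class rather than for this combination. Table 8 gives 7% for grade 3 to 4 increased creatinine, which includes grade 4 and is not limited to immune-mediated cases. Neither figure measures a conflict.

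**The case against.** The best reply is that the roles are already clear. Section 7.4 is the pembrolizumab modification section, it rests on prescribing information and cites only Table 4, and Appendix 2 is brought in for supportive care. That is the natural reading, and it stands as an inference. It does not close the gap, because a site that uses a table titled dose modification, with an action column, to decide on dosing is using it as labelled.

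A second reply is that a cautious site can comply by applying the stricter cell in each row. For myocarditis this works: resumption in Appendix 2 is permissive, so a permanent stop breaches nothing. For nephritis it means withholding drug that the Table 4 footnote would resume. In neither case does the protocol tell the site to do this.

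A third reply points to safeguards. Appendix 2 sets a condition before any restart: "Corticosteroid taper should be initiated upon AE improving to Grade 0 or 1 and continue to taper over at least 4 weeks". SAEs, unanticipated problems and qualifying toxicities go to the principal investigator and Coordinating Center within 1 business day, the team meets at least monthly, and the DSMC reviews safety. These reduce the risk, but none is an approval step for rechallenge.

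Four stronger readings are tempting, and the documents do not support them:

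- **Grade 2 events escape expedited reporting unless they are SAEs.** Table 5 has two other routes, one of which (qualifying toxicities) is not defined in the available text. The SAE definition also admits important medical events by judgment.
- **Treatment at a non-study site adds to the risk.** Study calendar note G says that the study team carries out the AE assessment in that case.
- **Hypothyroidism is a third conflict.** Appendix 2 has a specific row and Table 4 a general endocrinopathy row; the specific is ordinarily read over the general.
- **The trial's estimates are materially biased.** The effect on 3.3.3 is small, and the ORR precision statement in Section 13.2 does not depend on these rules.

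**Conclusion.** The inconsistency is real and should be fixed. It consists of two incompatible cells plus a difference in the starting point of the 12-week clock, all in current text. Its weight lies in safety, through possible rechallenge after grade 2 myocarditis, and in uniform conduct across up to 10 sites. The statistical effect is small: at most 1 percentage point on 3.3.3 per affected patient at 100 patients, with the two cells working in opposite directions.

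This rests on three assumptions. The events are rare, which the documents suggest but do not quantify for these cells. Grades mean the same in both tables: Appendix 2 is headed CTCAE v4.0 while Section 7.2 specifies v5.0, and Table 4 grades creatinine where Appendix 2 grades nephritis and renal dysfunction. Stopping pembrolizumab counts as discontinuing treatment for 3.3.3; if it does not while lenvatinib continues, the effect is smaller still.

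**What to change.** 1. State in Sections 7.4 and 6.3.1 that Table 4 governs pembrolizumab withhold and discontinue decisions wherever it differs from Appendix 2.
2. State that the Appendix 2 discretion note does not override a permanent discontinuation in Table 4.
3. Correct the Appendix 2 cells: grade 2 myocarditis to permanent discontinuation, grade 3 nephritis to withhold. If the sponsor prefers the stricter nephritis rule, change Table 4 instead, so that both agree; that clinical choice belongs to the sponsor.
4. Start the 12-week limit for event resolution at initiation of steroids in both places.
5. Keep the Appendix 2 rules on which Table 4 is silent, such as grade 1 myocarditis and recurrent grade 2 pneumonitis.
6. As an editorial change, relabel the Appendix 2 grade column to CTCAE v5.0 to match Section 7.2.

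The cost is amendment wording and IRB approval. No visits, staff or patients are added, and eligibility does not change.

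### The 12-week limit for permanently stopping pembrolizumab runs from steroid initiation in the Table 4 footnote but from the last dose in Appendix 2, and nothing says which governs

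*Combined protocol and SAP*

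**What the plan says.** Two places in the protocol set time limits after which withheld pembrolizumab is to be stopped for good.

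**Section 7.4 and Table 4.** The † footnote to Table 4 allows restart on this condition: "Resume in patients with complete or partial resolution (grades 0 to 1) after corticosteroid taper". It then sets two limits. For the reaction itself: "Permanently discontinue if no complete or partial resolution within 12 weeks of initiating steroids". For the steroid dose: "inability to reduce prednisone to 10 mg per day or less (or equivalent) within 12 weeks of initiating steroids". The body text of Section 7.4 gives only the steroid-dose limit, with the same start: "inability to reduce corticosteroid dose to 10 mg or less of prednisone or equivalent per day within 12 weeks of initiating steroids".

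**Appendix 2, general instructions.** The restart condition is much the same: "pembrolizumab can be resumed after AE has improved to grade 0 or 1 and corticosteroid has been tapered". The limit for the reaction has a different start: "Pembrolizumab should be permanently discontinued if AE does not resolve within 12 weeks of last dose". The limit for steroids has no stated start: "corticosteroids cannot be reduced to ≤ 10 mg prednisone or equivalent per day within 12 weeks". A note at the end of the appendix adds: "Withholding or permanently discontinuing pembrolizumab is at the discretion of the investigator or treating physician".

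Section 7.4 sends the reader to Table 4. Section 6.3.1 sends the reader to Appendix 2 for immune-related events, and that appendix's title covers dose modification as well as toxicity management. No section says which text prevails.

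**The concern.** The decision and the length of the limit are the same in both places, but the clock starts on different dates. Steroids normally start some time after the last infusion, so the Appendix 2 limit usually falls earlier. A patient who improves between the two limits could be restarted by a site working from Table 4 and permanently discontinued by a site working from Appendix 2.

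The trial runs at up to 10 sites, so different readings are a practical possibility. Time to drug discontinuation is a safety outcome in Section 13.1, and Section 3.3.3 counts patients who discontinue because of treatment-related adverse events. If sites apply different limits, these results partly reflect which page was used.

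**Working it through.** The plan gives no figure to reproduce here. The check is a comparison of the texts plus date arithmetic.

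**Inputs from the protocol**
- Both limits: 12 weeks = 84 days (Table 4 footnote †; Appendix 2).
- Pembrolizumab on day 1 of each 21-day cycle (Section 6.2); visits ±3 days, continuing on schedule while drug is held (Section 12).
- Taper starts at grade 0 or 1 and lasts at least 4 weeks (Appendix 2).
- Initial prednisone 1–2 mg/kg for several events and 0.5–1 mg/kg for liver events (Appendix 2).

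**Assumptions**
- The gap *g* from last dose to steroid start is not given, so a range is shown.
- Body weight 70 kg; a linear taper to zero over the minimum 4 weeks; the full starting dose held until taper begins.

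**Step 1. The resolution clocks alone.** Let *T* be days from last dose to grade 0–1. Table 4 is met if *T* − *g* ≤ 84. Appendix 2 is met if *T* ≤ 84. They disagree when 84 < *T* ≤ 84 + *g*, that is, on *g* days. At *g* = 0 there is no disagreement. At *g* = 21, the Appendix 2 limit falls 84 − 21 = 63 days (9 weeks) after steroid start, against 12 weeks in Table 4.

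**Step 2. Add the 10 mg limit.** Let *r* be the days from start of taper until the dose reaches 10 mg. To reach 10 mg within 84 days of steroid start, taper must begin by day 84 − *r* on the steroid clock. For a linear 28-day taper from dose *D*, *r* = 28 × (1 − 10/*D*):
- *D* = 35 mg (0.5 mg/kg): *r* = 20 days, so taper by week 9.1
- *D* = 70 mg (1 mg/kg): *r* = 24 days, so taper by week 8.6
- *D* = 140 mg (2 mg/kg): *r* = 26 days, so taper by week 8.3

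On the same clock, the Appendix 2 resolution limit is day 84 − *g*. If the Appendix 2 steroid limit is also read as running from steroid initiation, the two texts then classify a patient differently only when *g* > *r*, over *g* − *r* days.

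| Gap *g* (days) | Days after last dose on which the resolution clocks disagree | Days left after the 10 mg limit: 35 / 70 / 140 mg |
|---|---|---|
| 7 | 85–91 (7) | 0 / 0 / 0 |
| 14 | 85–98 (14) | 0 / 0 / 0 |
| 21 | 85–105 (21) | 1 / 0 / 0 |
| 42 | 85–126 (42) | 22 / 18 / 16 |

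A front-loaded taper shortens *r*. If 10 mg is reached 14 days into the taper, a 21-day gap leaves 21 − 14 = 7 days of disagreement.

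**Step 3. A course on which the texts differ.** A dose is withheld on day 21. A †-marked reaction is found and steroids start at 70 mg on day 42. Grade 1 is reached on day 91. That is 91 − 42 = 49 days of steroids, and the dose reaches 10 mg on steroid day 49 + 24 = 73. Both Table 4 limits are met. But day 91 is past 84 days from last dose, so Appendix 2 calls for permanent discontinuation.

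**Step 4. The steroid limit.** Table 4 and Section 7.4 count from steroid initiation; Appendix 2 names no start. If a reader took it to be the last dose, the latest taper start under Appendix 2 would be 84 − *g* − *r*, against 84 − *r* under Table 4, and the full gap of *g* days would return. The text does not settle this, so this limit is ambiguous rather than contradictory.

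**The case against.** The best reply is that the difference between clocks is not a difference in who stops. Take a patient with a 21-day gap who reaches grade 1 at week 10 of steroids. Table 4 seems to allow restart and Appendix 2 does not. But two weeks remain to reach 10 mg, and halfway through a linear 4-week taper the dose is 35–70 mg from 70–140 mg, or 17.5 mg from 35 mg. The footnote's own steroid limit would stop that patient too. This stands, and it removes most of the disagreement for gaps within one cycle under the taper assumed. It does not remove it for longer gaps, low starting doses or faster early reductions.

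A reader might also infer more than the documents support:
- *That one text compels stopping while the other permits restart.* Appendix 2 says should, and its closing note leaves the decision to the physician. Table 4 is headed as recommended modifications, and Section 7.4 opens with a general qualifier. Neither text is absolute. The discretion note does not cure the mismatch, though: it appears only in Appendix 2, names no clock, and does not say whether it reaches Table 4.
- *That every withheld immune-related event is affected.* The footnote applies only to rows marked †. Endocrinopathies are not marked, and Appendix 2 gives grade 3 or 4 cases their own restart condition.
- *That Section 7.4 as a whole contradicts Appendix 2.* Its body text sets no limit for resolution of the reaction.
- *That the 49% with pembrolizumab interrupted in the cited trial (Section 9.2.11) measures the exposure.* That figure covers any adverse reaction, with fatigue the most frequent at 14%.

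The trial is single-arm, so no between-arm bias arises. Section 3.3.3 also does not say whether stopping pembrolizumab while continuing lenvatinib counts as discontinuing treatment.

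**Conclusion.** The inconsistency holds for the limit on resolution of †-marked reactions: Table 4 footnote † and Appendix 2 start the same 12 weeks on different dates. The limits differ by exactly the gap from last dose to steroid start, which is 0–3 weeks within one cycle (18–24 days if found at the next day 1 visit, given the ±3-day window) and about 6 weeks after one withheld dose. For steroid reduction the texts are ambiguous, not opposed.

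The number of patients affected cannot be derived from the documents. On the taper assumptions above, and with the Appendix 2 steroid limit read from steroid initiation, it is probably small for gaps up to about 3 weeks and larger beyond that. With 100 patients, each one classified differently moves a discontinuation proportion by one percentage point. The effect on time to drug discontinuation is direct; the effect on the Section 3.3.3 count is possible but depends on how that endpoint treats stopping one drug. The primary endpoint analysis is not at issue here. It remains worth correcting because it is a safety-relevant rule that reads two ways and is cheap to align.

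**What to change.** Reconcile footnote † of Table 4, the Section 7.4 text and the Appendix 2 general instructions:
1. Give the resolution limit and the steroid-reduction limit one stated clock start each, the same in every place.
2. Use the same resolution wording throughout. The footnote defines it as grade 0 to 1; the Appendix 2 stopping rule says only resolve.
3. State whether the closing discretion note in Appendix 2 applies to these limits.
4. Record the dates of last pembrolizumab dose, steroid start and return to grade 0–1, so that adherence to the rule can be checked. The third may need its own field, because Section 8.4 allows only the highest grade to be entered when a toxicity fluctuates.

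Which clock applies is for the sponsor and clinical team to decide. The cost is a wording amendment and three dates on the case report form; the design, sample size and primary analysis do not change.
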